However, study durations are limited and long-term efficacy and safety is also limited. The pasireotide-induced effects of long-term hyperglycemia and other potential long-term effects (i.e. on GH/IGF-1 axis) could not be addressed by the pivotal trial [[CSOM230B2305](#)]. As Health Authorities require such data, the purpose of this non-interventional study is therefore to generate long term safety and efficacy data during the long-term treatment of pasireotide s.c. in patients with Cushing's disease in a real life setting.

2 Study objectives

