3.2 Discussion of design

This is a non-interventional, multinational, multi-center post-marketing study, to further document the safety/tolerability and efficacy of pasireotide s.c. in patients with Cushing's disease.

This study is observational in nature and does not impose a therapy protocol, diagnostic/therapeutic interventions or a visit schedule. Patients with Cushing's disease who are treated with pasireotide s.c. will be followed up for 3 years from patient's enrollment into this study, unless the patient discontinues pasireotide s.c. prematurely. If patients discontinue pasireotide s.c. prior to completing the 3 year observation period then any available safety and efficacy parameter will be collected until 3 months after the last dose of pasireotide s.c.

The timeframe of 3 years will allow to investigate the long-term safety/tolerability and efficacy of pasireotide s.c. including important safety evaluation on pasireotide s.c.-induced glycaemia effects, as well as the long-term changes of pituitary hormones and their by-products. The 3 year observation period is long enough to allow for the stabilization of the biochemical measures of disease activity (i.e. UFC and plasma ACTH), thus reducing the confounding effect of acute changes in UFC on the long-term safety measures (such as glycaemia, and pituitary hormones).

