3.5.2.6 Glucose metabolism

Alterations in blood glucose levels have been frequently reported in healthy volunteers and patients treated with pasireotide. Hyperglycaemia and, less frequently, hypoglycaemia, were observed in subjects participating in clinical studies with pasireotide s.c.

The degree of hyperglycaemia appeared to be higher in patients with pre-diabetic conditions or established diabetes mellitus. During the pivotal study, HbA1c levels increased significantly and stabilized but did not return to the baseline values. Less cases of discontinuation and lower reporting rate of severe AEs due to hyperglycaemia have been reported in patients treated with the dose of $600\mu\text{g}$ b.i.d.

The development of hyperglycaemia appears to be related to decreases in secretion of insulin (particularly in the post-dose period) and of incretin hormones (i.e. glucagon-like peptide-1 [GLP-1] and glucose-dependent insulinotropic polypeptide [GIP]).

Glycaemic status (fasting plasma glucose/haemoglobin A_{1c} [FPG/HbA_{1c}]) should be assessed prior to starting treatment with pasireotide s.c. FPG/HbA_{1c} monitoring during treatment should follow established guidelines. In addition, monitoring of FPG 4 weeks and HbA_{1c} 3 months after the end of the treatment is recommended. Self-monitoring of blood glucose and/or FPG assessments should be done every week for the first two to three months and periodically thereafter, as clinically appropriate.

If hyperglycemia develops in a patient being treated with pasireotide s.c., the initiation or adjustment of antidiabetic treatment is recommended, following the established treatment guidelines for the management of hyperglycemia. In the majority of patients who developed hyperglycaemia, the condition appeared to be manageable with appropriate antidiabetic therapy. If uncontrolled hyperglycaemia persists despite appropriate medical management, the dose of pasireotide s.c. should be reduced or pasireotide s.c. treatment discontinued.

Cushing's disease patients with poor glycaemic control (as defined by HbA_{1c} values $>8\%$ while receiving antidiabetic therapy) may be at higher risk of developing severe hyperglycaemia and associated complications. In patients with poor glycemic control the diabetes management should be intensified prior to initiation and during pasireotide therapy.

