3.5.2.12 Concomitant medications including significant non-drug therapies

All concomitant medications and significant non-drug therapies (e.g., surgery, radiation) will be recorded in this study on an ongoing basis. This will also include any information on antidiabetic treatment.

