6.5.2.2 Laboratory evaluations

All laboratory values will be converted into SI units.

The frequency of laboratory abnormalities will be summarized for each parameter. Laboratory data will also be summarized via shift tables. A listing of laboratory values will be provided by laboratory parameter, patient and visit window. No imputation for missing values will be done for laboratory variables and they will be identified as missing.

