6.5.2.3 Other safety data

Available data from other tests (e.g. vital signs, glucose metabolism evaluations, ECG, and gallbladder imaging) will be summarized descriptively by visit window. Shift tables will be provided as appropriate. No imputation for missing values will be done for those variables and they will be identified as missing.

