#### **8.4.2 Laboratory evaluation**

All laboratory values will be converted into SI units.

Laboratory data will be classified (by biostatistics/SAS programming) into CTC grades according to the NCI Common Terminology Criteria for Adverse Events (CTCAE) v3.0. A severity grade of 0 will be assigned when the value is within normal limits. In the unlikely case when a local laboratory normal range overlaps into the higher (i.e. non-zero) CTC grade, the laboratory value will still be taken as within normal limits and assigned a CTC grade of zero.

For some laboratory tests, CTC grades are defined in two directions (low and high, e.g. for potassium: hypokalemia and hyperkalemia). The two directions will be analyzed separately.

The following summaries will be produced for the laboratory data (by laboratory parameter and direction of abnormality, as applicable):

- Shift tables using CTC grades to compare baseline to the worst post-baseline value
- Shift tables using CTC grades to compare the last post-baseline grade on treatment to the worst grade during the 90 days after permanent discontinuation of pasireotide s.c., in patients who discontinued pasireotide s.c. prematurely.
- For laboratory parameters where CTC grades are not defined, shift tables to the minimum and maximum post-baseline value using the low/normal/high classifications based on laboratory reference ranges.

Patients with laboratory values outside the laboratory reference range will be listed and flagged to show the corresponding CTC grades and the classifications relative to the laboratory reference ranges. In addition, laboratory values of patients with laboratory abnormalities of CTC grade 3 or 4 will be presented in separate listings.

HbA1c values will be classified into categories <5.7%, >=5.7% - <6.5% >=6.5% - 8% and >=8%, and categories cross-tabulated in shift tables (baseline versus worst post-baseline category).

---

Study Code: CSOM230B2410

A similar analysis will be performed for fasting glucose, classified into categories <100 mg/dL, >=100-<126 mg/dL, >=126 mg/dL (baseline versus worst post-baseline category).

The analyses of glucose will only include patients who were fasting at the time of blood sampling.

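### SAP 8.4.2 lists only baseline-versus-worst shift tables for HbA1c and fasting glucose, although protocol 6.5.2.3 requires a summary by visit window.

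*SAP*

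**What the plan says.** **Purpose.** Protocol Section 1 names the effects of long-term hyperglycaemia as an open question and adds that "other potential long-term effects (i.e. on GH/IGF-1 axis) could not be addressed by the pivotal trial". It continues: "As Health Authorities require such data, the purpose of this non-interventional study is therefore to generate long term safety and efficacy data". Protocol 3.2 justifies the 3-year period as "including important safety evaluation on pasireotide s.c.-induced glycaemia effects, as well as the long-term changes of pituitary hormones and their by-products".

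**Protocol analysis plan.** For glucose, protocol 6.5.2.3 is specific: "Available data from other tests (e.g. vital signs, glucose metabolism evaluations, ECG, and gallbladder imaging) will be summarized descriptively by visit window". For laboratory parameters in general, protocol 6.5.2.2 says: "The frequency of laboratory abnormalities will be summarized for each parameter. Laboratory data will also be summarized via shift tables". It adds a listing of values by parameter, patient and visit window. GH, IGF-1, TSH and free T4 are among the laboratory parameters in protocol 3.5.2.8.

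**SAP.** Section 8.4.2 places HbA1c in four classes, with "categories cross-tabulated in shift tables (baseline versus worst post-baseline category"), and treats fasting glucose the same way in three classes. Other laboratory parameters get shifts in CTC grade from baseline to the worst value. Where no CTC grade exists, they get low/normal/high shifts to both the minimum and the maximum. Values are listed for patients with a result outside the reference range. Section 3, on changes in the planned analysis, is marked not applicable. Section 4.1 repeats the general rule of displaying data by time window and adopts protocol Section 6 by reference.

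**The concern.** Every other item that protocol 6.5.2.3 names as an example has a by-window output in the SAP. Temperature and pulse have one in 8.4.3, ECG in 8.4.4 and gallbladder imaging in 8.4.5; blood pressure and weight have theirs in 8.2.1.4. Even lipids get change by window (8.2.1.2). Glucose, the one closest to the reason for the study, does not.

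At stake is whether the report can say that HbA1c rises, plateaus or recovers over 36 months. Protocol 3.5.2.6 already reports that HbA1c rose and then stabilised without returning to baseline in the pivotal study, so the open question is the later course. Protocol 3.2 also argues that 3 years lets UFC stabilise, so that acute changes confound the long-term safety measures less. A worst-ever table mixes the early, unstable phase with the later one and loses that advantage.

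**Working it through.** The documents give no figure to reproduce here. The check is a comparison of texts, followed by an illustration.

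**1. Outputs set side by side**

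| Parameter | Protocol plan | SAP output on treatment |
|---|---|---|
| HbA1c, fasting glucose | By visit window (6.5.2.3) | Baseline versus worst class only (8.4.2) |
| GH, IGF-1, TSH, free T4 | Abnormality frequencies, shift tables, listing by window (6.5.2.2) | Shift tables; listing limited to patients with out-of-range values (8.4.2) |
| Temperature, pulse | By visit window (6.5.2.3) | Change by window (8.4.3) |
| ECG | By visit window (6.5.2.3) | Values and change by window (8.4.4) |
| Gallbladder imaging | By visit window (6.5.2.3) | Frequencies by window (8.4.5) |

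A commitment specific to glucose is therefore not carried into the list of outputs. For the hormones, the only specific item not carried into 8.4.2 is the by-window listing of all values. SAP 2.2.1 keeps a laboratory listing by patient for the interim analyses, but does not say it is by window.

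**2. What a worst-value shift can show**

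Take two patients who both start in the class from 5.7% to below 6.5%. One has a single value in the next class at Month 3 and then returns. The other stays in that class to Month 36. Both fall in the same cell.

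The worst of k values cannot improve when a further value is added. The table therefore depends on how long and how often a patient was measured. SAP 8.4.1 recognises that exposure differs between cohorts and adjusts the adverse event rates for it; the worst-value tables carry no such adjustment.

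**3. Illustration of size**

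Inputs:
- Values per patient, k: 12 over 36 months at the suggested 3-monthly HbA1c (protocol Table 3-1; 36/3 = 12), and 4 over one year (12/3 = 4). SAP Table 6-2 has 9 post-baseline windows up to Month 36.
- Distance from the true value to the class limit: 0.3 points (for example true 6.2%, limit 6.5%). Assumed.
- Within-patient SD: 0.1, 0.2 or 0.3 points. Assumed; the documents give none.
- Values independent and normal around a constant true level. Assumed.

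Formulas: p = 1 − Φ(0.3/SD) for a single value; P(worst of k crosses) = 1 − (1 − p)^k.

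| SD | 0.3/SD | p (k = 1) | k = 4 | k = 9 | k = 12 |
|---|---|---|---|---|---|
| 0.1 | 3.0 | 0.001 | 0.005 | 0.012 | 0.016 |
| 0.2 | 1.5 | 0.067 | 0.242 | 0.463 | 0.564 |
| 0.3 | 1.0 | 0.159 | 0.499 | 0.789 | 0.874 |

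For SD 0.3 and k = 12: 1 − 0.841^12 = 0.87. With the true value 0.5 points below the limit (6.0%) and SD 0.3, the figures for k = 1, 4 and 12 are 0.05, 0.18 and 0.44.

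**4. Class limits**

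The two upper HbA1c classes in SAP 8.4.2 run from 6.5% to 8% and from 8% upward, with the second including 8%. As written, a value of exactly 8.0% fits both.

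**The case against.** **SAP 4.1 already covers it.** It repeats the general window rule and adopts protocol Section 6, so 6.5.2.3 formally still applies. This stands as far as it goes, and it is why a reader who infers that the glycaemic course has been abandoned, or will never be reported, goes further than the documents allow. But SAP 2 says the plan describes all planned analyses, SAP 4.1 points to later sections for the details, and 8.4.2 lists its outputs without this one. The SAP is then internally inconsistent, which also needs correcting.

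**Other outputs have a time element.** Adverse events of special interest, including hyperglycaemia and growth hormone deficiency categories, are tabulated by interval of onset (SAP 8.4.1). Change after stopping is examined in early discontinuers (SAP 8.4). These outputs exist, but onset counts do not show level or recovery. Under protocol 3.5.2.1, an abnormal laboratory value is an adverse event only if it causes signs or symptoms, is clinically significant or needs therapy. The change after stopping is not the on-treatment course.

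**The hormones.** A reader might infer that the SAP dropped a by-window hormone summary as well. It did not: protocol 6.5.2.3 does not name hormones, and 6.5.2.2 plans abnormality frequencies and shift tables for laboratory data. Where no CTC grade exists, the shift to the minimum would also show a fall below normal; only its timing is missing.

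**Antidiabetic treatment.** The protocol collects it ("This will also include any information on antidiabetic treatment") and refers to it in a clinical caution that patients with HbA1c above 8% "while receiving antidiabetic therapy) may be at higher risk of developing severe hyperglycaemia". Neither document promises HbA1c tabulated by treatment status, and that caution is not an analysis class that the SAP must match. Concomitant medications are summarised by ATC class (SAP 4.2.5). The cross-classification is an optional addition, not an omission.

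**The probabilities rest on assumptions.** This is right. Positive correlation between values, fewer measurements (the schedule is only suggested) or a true level further from the limit would all lower them. The direction of the effect does not depend on them.

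**Conclusion.** The point holds for HbA1c and fasting glucose. A by-window summary named in the protocol is missing from the SAP's laboratory outputs, with no declared change, on a question the protocol gives as a reason for the study. For GH, IGF-1, TSH and free T4 the gap is one of design: it begins in protocol 6.5.2.2, but the planned outputs still fall short of the aim in protocol Sections 1 and 3.2. The overlap at 8.0% is a small, definite wording error.

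The numerical size is not known from the documents. In the illustration, the chance that a stable patient 0.3 points below a limit is classed above it after 12 values runs from about 2% (SD 0.1) to 87% (SD 0.3). This shows sensitivity to the number of measurements; it does not predict the study's tables or show that longer-followed patients will look worse for this reason alone.

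This should be fixed, but it is not critical. The primary endpoint of pasireotide-related adverse events and serious adverse events is unaffected, the study is exploratory, and the data are already collected.

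**What to change.** In SAP 8.4.2:

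1. Add observed value and absolute change from baseline by Table 6-2 window, overall and by cohort, for HbA1c and fasting glucose, as protocol 6.5.2.3 requires.
2. As a cheap improvement, add the same for GH, IGF-1, TSH and free T4. Protocol Table 3-1 suggests these at 6- or 12-month intervals, so the SAP should say whether Table 6-2 or, under its own rule in 6.1.7, Table 6-3 applies.
3. Keep the worst-value shift tables as a supplement.
4. Make the upper HbA1c classes mutually exclusive at 8%.
5. Optionally, show HbA1c class by antidiabetic treatment status.

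If the by-window glucose summary is deliberately left out, record that in SAP 3 with the reason.

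The cost is a few extra tables and no new assessments. Counts in late windows may be thin, so each table should show the number of patients per window.

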#### 8.4.3 Vital signs and weight

Vital signs (body temperature, sitting pulse, sitting blood pressure), weight and waist circumference will be summarized and listed. Patients with clinically notable vital sign values will be flagged in the listing.

The criteria for clinically notable abnormalities are defined as follows:

- Systolic BP:  $\geq 180$  mmHg and an increase  $\geq 20$  mmHg from baseline  
 $\leq 90$  mmHg and a decrease  $\geq 20$  mmHg from baseline
- Diastolic BP:  $\geq 105$  mmHg and an increase  $\geq 15$  mmHg from baseline  
 $\leq 50$  mmHg and a decrease  $\geq 15$  mmHg from baseline
- Pulse rate:  $\geq 120$  bpm with increase from baseline of  $\geq 15$  bpm  
 $\leq 50$  bpm with decrease from baseline of  $\geq 15$  bpm
- Body temperature:  $\geq 39.1^\circ\text{C}$   
 $\leq 35^\circ\text{C}$
- Weight: Increase from baseline of  $\geq 10\%$   
decrease from baseline of  $\geq 10\%$

The following summaries will be produced for each parameter for which notable abnormalities are defined:

- Frequency table of notable values assessed on treatment after baseline
- Shift table comparing the last post-baseline value on treatment to the worst value (i.e. highest value and lowest value) during the 90 days after permanent discontinuation of pasireotide s.c., in patients who discontinued pasireotide s.c. prematurely.

Furthermore for body temperature and sitting pulse, absolute and percentage change from baseline will be summarized with descriptive statistics by time window. Similar summaries were done for blood pressure, weight and waist circumference as part of the efficacy analyses.

#### 8.4.4 ECG

The following analyses will be performed for RR, PR, QT intervals and QRS duration, ventricular rate, QTcB (Bazett's formula) and QTcF (Fridericia's formula):

---

Study Code: CSOM230B2410

- Summary statistics at baseline and for each time window,
- Summary statistics of changes from baseline for each time window,
- Listing of ECG data .

Number (%) of patients with a notable QT interval, based on both QTcB and QTcF will be summarized by cohort at any time post-baseline. ECG shift table based on notable values will be summarized by treatment group. Notable criteria for QTcB/QTcF include:

- >450 ms at any time post-baseline and  $\leq$  450 ms at baseline,
- >480 ms at any time post-baseline and  $\leq$  480 ms at baseline,
- >500 ms at any time post-baseline and  $\leq$  500 ms at baseline,
- An increase from baseline > 30 ms at any time post-baseline ,
- An increase from baseline > 60 ms at any time post-baseline .

Patients with notable QT interval values or any clinically significant ECG abnormality will be flagged in the listings.

Above analyses will be performed for patients who discontinued pasireotide s.c. prematurely comparing the last post-baseline value on treatment to the worst value during the 90 days after permanent discontinuation of pasireotide s.c.

#### 8.4.5 Gallbladder ultrasound

The findings of the gallbladder imaging (presence of gallstones, presence of sludge, dilatation of ductal system, thickening) will be summarized using frequency tables by time window (Month 6, 12, 18, 24, 30, and 36) and shift tables. In the shift tables, the last post-baseline result on treatment will be tabulated against the baseline result.

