3.1.1 Safety and tolerability assessments

All safety assessments will be collected from patient's enrollment into the study by signing the informed consent or acknowledging an equivalent document (e.g., written information) as per country regulation until the last dose of pasireotide s.c. at the patient's last follow-up visit within the 3 year observation period or until 3 months after the last dose for patients who permanently discontinue pasireotide s.c. prior to completing 3-year observation period.

- Adverse events and Serious Adverse Events will be followed-up and collected from patient's enrollment into the study until 28 days after the last dose of pasireotide s.c. at the patient's last follow-up visit. Adverse events and Serious Adverse Events will be collected until 3 months after the last dose for patients who permanently discontinue pasireotide s.c. prior to completing 3-year observation period.
- Special safety assessments will be collected from patient's enrollment into the study until the last follow-up visit as available or until 3 months after the last dose for all available safety parameters, for patients who permanently discontinue pasireotide s.c. prior to completing the 3-year observation period. Safety data to be collected include: vital signs, blood pressure, heart rate, body temperature, blood glucose (fasting plasma glucose, HemoglobinA1c), hormones (IGF-1, GH, TSH/free T₄), liver enzymes (AST, ALT, alkaline phosphatase, γGT, total bilirubin), hematology, electrolytes, immunological events (e.g., allergic reactions: rash, pruritus, injection site reactions), gallbladder ultrasound and ECGs.
- Medical history including history of smoking, history of alcohol use, presence of hepatitis B and C infection will be recorded at patient's entry in the study. Prior/concomitant medications/significant non-drug therapies (e.g., surgery, radiation) will be collected from patient's enrollment into this study until the last follow-up visit as available or until 3 months after the last dose for patients who permanently discontinue pasireotide s.c. prior to completing the 3-year observation period.

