3.5.2.11 Gallbladder ultrasound

Cholelithiasis is a recognised adverse reaction associated with long-term use of somatostatin analogues and has frequently been reported in clinical studies with pasireotide s.c. Ultrasonic examination of the gallbladder before and at 6- to 12-month intervals during pasireotide s.c. therapy is therefore recommended. The presence of gallstones in pasireotide s.c.-treated patients is largely asymptomatic; symptomatic stones should be managed according to clinical practice.

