**Table 6-3 Time windows for analyses of tumor volume, patient reported outcome variables and gallbladder ultrasound**

Window name (1)	Window No.	Target Day	Starting Day of Window	Ending Day of Window
Baseline	1	-	-	1 (2)
Month 6	4	183	137	320
Month 12	6	365	321	458
Month 18	7	550	459	641
Month 24	8	731	642	821
Month 30	9	914	822	1005
Month 36	10	1096	1006	1187
After Month 36	11	-	1188	No upper limit
Last value on treatment		DLD (3)	2	DLD + gap (4)
Day 90 after last dose		DLD + 90 days	DLD+gap+1 days	DLD + 90 days

(1) Windows are named according to their target days. For example, the target day for window Month 6 is  $6 * 30.4375$  days, where 30.4375 is the standard length of a month ( $=365.25/12$ ). The starting day of the window is the midpoint between target day of previous window and current window and the ending day is the midpoint between target day of current window and next window.  
 Note that only post-baseline on-treatment assessments are assigned to windows Month 6, Month 12, etc., up to 'after Month 36'.  
 (2) For some parameters, the earliest assessment after first dose is used as baseline assessment if no assessment is available before or on the day of first dose. This assessment is then exclusively used as baseline assessment although it falls into a post-baseline window.  
 (3) DLD = Day of last dose of pasireotide s.c.  
 (4) gap = number of days after DLD during which assessments and events are considered on-treatment. gap=3 for efficacy analyses, gap=28 for safety analyses

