## 9.2 AESI LIST

Category	Adverse Event Term
AESI Bradycardia related AEs	Atrial conduction time prolongation (PT) Atrioventricular block (PT) Atrioventricular block complete (PT) Atrioventricular block second degree (PT) Atrioventricular dissociation (PT) Bradycardia (PT) Central bradycardia (PT) Conduction disorder (PT) Defect conduction intraventricular (PT) Electrocardiogram PQ interval prolonged (PT) Electrocardiogram PR prolongation (PT) Electrocardiogram QRS complex prolonged (PT) Electrocardiogram QT prolonged (PT) Long QT syndrome (PT) Paroxysmal atrioventricular block (PT) Sinoatrial block (PT) Sinus bradycardia (PT)
AESI Coagulation related AEs	Blood fibrinogen decreased (PT) Blood thrombin decreased (PT) Blood thromboplastin abnormal (PT) Blood thromboplastin decreased (PT) Coagulation factor IX level decreased (PT) Coagulation factor V level decreased (PT) Coagulation factor VII level decreased (PT) Coagulation factor X level decreased (PT) Coagulation factor decreased (PT) Hypofibrinogenaemia (PT) International normalised ratio abnormal (PT) Prothrombin level decreased (PT) Prothrombin time prolonged (PT) Prothrombin time ratio decreased (PT) Thrombin time prolonged (PT)
AESI Gallbladder and biliary related AEs	Bile duct necrosis (PT) Bile duct obstruction (PT) Bile duct stenosis (PT) Bile duct stone (PT) Bile output abnormal (PT) Bile output decreased (PT)

Study Code: CSOM230B2410

Category	Adverse Event Term
	Bile output increased (PT)
	Biliary cirrhosis (PT)
	Biliary colic (PT)
	Biliary dilatation (PT)
	Biliary dyskinesia (PT)
	Biliary dyspepsia (PT)
	Biliary fibrosis (PT)
	Biliary fistula (PT)
	Biliary ischaemia (PT)
	Biliary tract disorder (PT)
	Bilirubin conjugated abnormal (PT)
	Bilirubin conjugated increased (PT)
	Bilirubin excretion disorder (PT)
	Bilirubin urine present (PT)
	Bilirubinuria (PT)
	Blood alkaline phosphatase abnormal (PT)
	Blood alkaline phosphatase increased (PT)
	Blood bilirubin abnormal (PT)
	Blood bilirubin increased (PT)
	Blood bilirubin unconjugated increased (PT)
	Cholangiogram abnormal (PT)
	Cholecystectomy (PT)
	Cholecystitis (PT)
	Cholecystitis acute (PT)
	Cholecystitis chronic (PT)
	Cholecystogram intravenous abnormal (PT)
	Cholecystogram oral abnormal (PT)
	Cholelithiasis (PT)
	Cholelithiasis migration (PT)
	Cholelithiasis obstructive (PT)
	Cholestasis (PT)
	Deficiency of bile secretion (PT)
	Endoscopy biliary tract abnormal (PT)
	Gallbladder disorder (PT)
	Gallbladder enlargement (PT)

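### The gallbladder shift table in SAP 8.4.5 uses the last on-treatment scan rather than the worst, and the section names no output for the off-drug window that Table 6-3 defines

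*SAP*

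**What the plan says.** SAP 8.4.5 plans two outputs for gallstones, sludge, ductal dilatation and thickening. First, the findings "will be summarized using frequency tables by time window (Month 6, 12, 18, 24, 30, and 36) and shift tables". Second, it defines those shift tables: "the last post-baseline result on treatment will be tabulated against the baseline result".

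Table 6-3, whose title names gallbladder ultrasound, sets the windows. The monthly windows take on-treatment scans only, and the on-treatment limit is last dose plus a gap: "gap=3 for efficacy analyses, gap=28 for safety analyses". The table also defines a Day 90 window running from the end of that gap to 90 days after last dose. SAP 4.1 says that early discontinuers have their safety parameters reported in the window for last dose plus 90 days, and SAP 8.4 says that post-treatment assessments will be analysed.

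The neighbouring sections work differently. SAP 8.4.2 specifies "Shift tables using CTC grades to compare baseline to the worst post-baseline value". SAP 8.4.4 applies its notable-QTc criteria at any time post-baseline. SAP 8.4.2, 8.4.3 and 8.4.4 each add a comparison of the last on-treatment result with the worst in the 90 days after discontinuation.

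In the protocol, section 3.5.2.3 lists cholelithiasis as an important identified risk. Section 3.5.2.11 describes gallstones on pasireotide as largely asymptomatic and adds: "Ultrasonic examination of the gallbladder before and at 6- to 12-month intervals during pasireotide s.c. therapy is therefore recommended". Section 3.1.1 collects special safety assessments, gallbladder ultrasound among them, "until 3 months after the last dose for all available safety parameters" in patients who stop early.

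**The concern.** For a risk that is mostly silent, imaging is the natural place to count new cases, and the shift table is the only imaging output that relates a patient's follow-up to that patient's own baseline. Built on the last on-treatment scan, it describes status at the end of treatment, not whether the finding ever arose. A patient with a clear baseline, sludge at Month 12 and a clear scan at Month 24 is tabulated as absent to absent.

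The off-drug side is left open. A patient who stops between scans may have the next one more than 28 days after the last dose. Protocol 3.1.1 collects that scan, but 8.4.5 names no table for it.

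At stake is the imaging estimate of how often an important identified risk newly appears, in a study whose primary objective is the long-term safety profile.

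**Working it through.** The documents give no gallstone rate, resolution rate or planned figure for this table, so there is nothing to reproduce. The check is a reading of the rules, some window arithmetic and one illustration.

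1. **Direction.** Take patients free of a finding at baseline who have at least one post-baseline on-treatment scan. Anyone positive on the last scan is positive on at least one scan, so the newly positive count by last scan is never above the count by any scan. The two are equal only if no new finding clears or is removed before the last scan.

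2. **Off-drug window.** With the safety gap of 28 days, on-treatment ends at last dose + 28 and the Day 90 window runs from last dose + 29 to last dose + 90. Length: 90 − 28 = 62 days. Neither output of 8.4.5 uses it.

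3. **Do the frequency tables fill the gap?** In part.
 - They report findings present in each window, not the number of patients newly positive among those free at baseline.
 - In Table 6-3 baseline ends on day 1 and Month 6 starts on day 137. A scan on days 2 to 136 enters no frequency table, and enters the shift table only if it is the last on-treatment scan (or not at all as post-baseline, if it served as a Cohort 2 baseline under Table 6-1).
 - SAP 6.1.7 keeps the scan closest to the target day. The Month 6 window runs from day 137 to day 320, which is 320 − 137 + 1 = 184 days, with target day 183. As an example, a clear scan on day 180 (3 days from target) displaces a scan showing stones on day 310 (127 days from target).
 - The window after Month 36 (from day 1188) is not among the six that 8.4.5 lists.
 - Sections 8.4.2 to 8.4.4 each specify a listing; 8.4.5 does not.

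4. **Do the adverse event tables fill the gap?** In part. Under Protocol 3.5.2.1 a test result is an adverse event only if it causes signs or symptoms, is considered clinically significant or requires therapy. Treated or significant cases enter, and SAP 9.2 lists cholelithiasis, cholecystitis and cholecystectomy among the terms of special interest. Asymptomatic findings judged not significant need not enter.

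5. **Illustration of size.** Let N be the number of patients, all assumed free of the finding at baseline and scanned afterwards; p the share with a new on-treatment finding; and r the share of those who are clear on the last on-treatment scan. Both p and r are assumptions.
 - Worst scan: N × p. Last scan: N × p × (1 − r). Difference: N × p × r.
 - N = 100, p = 20%, r = 25%: 20 by worst scan, 20 × 0.75 = 15 by last scan, difference 5.
 - N = 100, p from 10% to 30%, r from 10% to 50%: difference from 100 × 0.10 × 0.10 = 1 to 100 × 0.30 × 0.50 = 15 patients.
 - N = 200, same ranges: 2 to 30 patients.

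 N = 100 and 200 are the planned minimum and maximum enrolment.

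**The case against.** The case for leaving 8.4.5 alone has several sound parts.

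- **Frequency tables exist.** A reader might infer that 8.4.5 assesses gallbladder risk by the last scan alone and that transient findings disappear. The text does not support that. Stones seen at Month 12 and gone by Month 24 are still counted in the Month 12 table if that scan is the one kept. What is lost is the link to baseline, plus the scans that fall outside or are displaced within the windows.
- **Serious cases are captured elsewhere.** A reader might also infer that the loss is greatest for stones that led to surgery or to stopping treatment. Across the whole safety report, the reverse is more likely. SAP 8.4.1 tabulates events of special interest by category, grade, type and time of onset, and separately summarises events leading to discontinuation or requiring additional therapy. Pre-existing conditions count as events only if they worsen, so these tables already relate to pre-treatment status. The under-reporting falls mainly on untreated, asymptomatic findings.
- **Off-drug reporting is foreseen.** SAP 4.1 and 8.4 and Table 6-3 all provide for it, and post-treatment adverse events are tabulated for early discontinuers. It would be too strong to say that the plan excludes off-drug scans. But 8.4 spells out only continuous parameters, gallbladder findings are categorical, and 8.4.5 names no table. A programmer working from 8.4.5 would produce none.
- **An end-of-treatment scan is suggested.** Protocol Table 3-1 marks gallbladder imaging at End of Treatment, and a scan within 28 days of the last dose enters the shift table. That narrows the off-drug gap. Protocol 3.5 imposes no visit schedule, so it does not close it.
- **There is no conflict with the protocol.** Protocol 6.5.2.3 asks only for descriptive summaries by visit window, with shift tables as appropriate, and requires the post-discontinuation comparison only for continuous safety variables. This stands: the point concerns the choice of analysis, not a breach of the protocol.

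**Conclusion.** The point holds for the imaging shift analysis. As written, the table can only match or undercount new gallbladder findings on treatment, and 8.4.5 names no output for the 62-day off-drug window that the SAP itself defines. The frequency and adverse event tables limit the consequence but do not replace a count of newly positive patients against baseline.

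The direction is certain and the size is not. The figures of 1 to 15 patients per 100, and 2 to 30 per 200, rest entirely on assumed values of p and r, and concern the shift table only. The primary endpoint is based on adverse events and this table does not enter it. This is a worthwhile, inexpensive improvement to a descriptive safety output.

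One further inference lacks support: that every post-baseline cholecystectomy can be read as gallstones. The documents do not show how a scan after cholecystectomy is recorded, and surgery may follow sludge or cholecystitis.

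**What to change.** In SAP 8.4.5:

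- Add, for each of the four findings, a shift table of baseline against the worst (any presence) on-treatment result. Report the number newly positive among those free of the finding at baseline and the number without a post-baseline scan.
- Add, for patients who discontinue early, a table of the last on-treatment result against the worst result in the Day 90 window, as 8.4.2 to 8.4.4 already do.
- Show patients with a cholecystectomy after baseline as a separate category, without imputing gallstones.
- Keep the last-value shift table as supplementary.

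The cost is SAP wording and one or two tables from scans already being collected. The reported percentage with gallbladder findings will be somewhat higher, so the text should say that it is an ever-on-treatment figure.
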